The research assistant will have at least a Bachelor's level education and the research therapists at least a Masters level education (or relevant experience) and previous experience in clinical rating and/or interviewing. Under the direct supervision of the principal investigators and/or data manager, the rater will receive one month of training on the assessments, including the PRISM CV-V. Training may include viewing videotapes, observation of interviews and ratings, co-rating and interviewing with the supervisor present. In order to conduct interviews for this study, it is required that the rater complete three consecutive conjoint interviews on which DSM V diagnoses are in complete agreement with those of more experienced raters. After training, reliability will be spot-checked on a semi-annual basis.

As for training on the other scales, the investigators and/or data manager first provides a training session on the background of the particular scale and how it is to be completed. Then the staff member observes the completion of the assessment by an experienced rater on at least 3 occasions. Afterwards, the staff member completes the assessment in the presence of an experienced rater on at least 3 occasions, with feedback given each time until the supervisor is confident that the person understands the assessment and completes it properly. Thereafter, assessments are checked on a continuous basis for appropriate completion and constructive criticism is given as necessary. Staff members also undergo a refresher on assessments every 6 months.

C. Collection and Reporting of Adverse Events (AEs) and Serious Adverse Events (SAEs).

All adverse events (AEs) occurring during the course of the study must be collected, documented, and reported to the PIs. The occurrence of AEs will be assessed in an ongoing way. Each week study investigators will review the AEs from the previous week for events that were reported as new or continuing. The study investigators will follow all AEs to the point of satisfactory resolution. A list of all AEs will be included in the annual progress report to NIDA.

The PIs and the Co-Investigators will determine whether an event meets the criteria of a serious adverse event (SAE) and/or an unanticipated problem involving risks to subjects or others (UPIRTSO). The PI will report AEs and SAEs on an annual basis and UPIRTSOs to the IRB in a timely fashion. The PI will report all SAEs such as deaths, hospitalizations and unexpected toxicity, whether or not study-related, to NIDA within 72 hours. The procedures for reporting these SAEs to NIDA include written documentation using the clinical notes related to the adverse event and specific forms detailing the event with a sign-off by all appropriate supervisory personnel. Outcomes of SAEs will be periodically reported to NIDA. A summary of the AEs, SAEs and UPIRTSOs that occurred during the year will be included in an annual report to NIDA.

The IRB communicates recommendations and decisions to the PI in a timely manner. In the event that the IRB takes an action that impacts the day-to-day operations of the trial (e.g., suspends recruitment, halts the trial), the PI will report those actions to the NIDA officer both verbally and in writing.

D. Data and Safety Monitoring (DSM) Plan

The PIs will be ultimately responsible for monitoring the safety and efficacy of the trial, executing the DSM plan, and complying with reporting requirements. The trial also has a study monitor, [name]. A Data and Safety Monitoring Board (DSMB) will also monitor this study. Members will be given a copy of the DSM plan prior to study initiation and will have the opportunity to make any recommendations at that time. DSM will occur in an ongoing way throughout the study. In addition, DSM will be formally reviewed when 33%, 67% and 100% of individuals have been enrolled. The PI will provide a summary of the DSM report to NIDA on an annual basis as part of the progress report. The DSM report will include a brief description of the trial, baseline sociodemographic characteristics, retention data, disposition of study participants, Q.A. issues, regulatory issues, AEs and SAEs along with assessments of attribution and severity, any actions or changes with respect to the protocol, and efficacy analyses, if conducted. This report will be given to the members of the DSMB for review when 33%, 67% and 100% of individuals have been enrolled or more frequently as necessary. The DSM Board will meet upon review of the DSM report generated when 33%, 67% and 100% of individuals have been enrolled or more frequently as necessary. Whether risks of participation remain acceptable under the present protocol or modifications to the protocol are necessary while still maintaining scientific integrity of the project will be determined. Interim analyses will not be performed unless clinically indicated. All SAEs, such as death, hospitalization, and unexpected toxicity, will be reported to the IRB, FDA, and NIDA under expedited reporting. The procedures for this reporting include written documentation using the clinical notes related to the adverse event and specific forms detailing the event with a sign-off by all appropriate supervisory personnel. We will report major protocol amendments or changes in the informed consent to NIDA, as well as any temporary or permanent suspension of patient accrual.

16. References:

1. Substance Abuse and Mental Health Services Administration, *Results from the 2009 National Survey on Drug Use and Health: Volume I. Summary of National Findings.*, N.S.H.-A. Office of Applied Studies, HHS Publication No. SMA 10-4856 Findings, Editor. 2010: Rockville, MD.

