During the detox phase, morning GBP/placebo ingestion will occur under supervision 6 days per week, and a take-home dose will be given each day for evening ingestion (3 take-home doses on Sat to also cover Sun). For participants on the truncated schedule due to COVID-19 (thrice weekly), lockboxes with BUP and GBP/Placebo will be given on the same schedule to be taken on days when not presenting to clinic (Tues, Thurs, weekends) with specific instructions provided by CAST nurse, in addition to drug accountability logs signed by the participant. Additional take-home doses of GBP/placebo will be given to take on holidays, days when clinic is closed due to inclement weather and holidays to ensure adequate blood levels of GBP are maintained. The initial dose of GBP at 100 mg will be given on day 3 of week 1, and a 100 mg dose provided to take home. The GBP dose will increase to 200 mg BID on day 4, 400 mg BID on day 5, 600 mg BID on day 6, and 800 mg BID (1,600 mg/day) on day 7 of week 1. Participants will remain on 1600 mg/day through day 2 of week 5 (during NTX therapy, GBP/placebo capsules will be given in weekly blister packs). Then GBP will be reduced to 1200 mg/day on day 3, 800 mg/day on day 4, 600 mg on day 5, 400 mg on day 6, and 200 mg on day 7. On days 1 and 2 of week 6, all participants will receive placebo. If GBP side effects are too severe at the 800-mg BID dose, GBP will be decreased to no less than 1200 mg/day, given data that 900 mg/day of GBP is ineffective [97]. If GBP side effects are too severe at 1200 mg/day, GBP will be discontinued and the participant will be discharged from the study and referred to local treatment agencies. During transition to NTX (week 4), if a) the participant's urine sample is opioid-negative and/or regular opioid use is not indicated, *and* b) orthostatic vital signs and symptoms are within limits specified below (Section 14, Protection of Participants, B. Protections Against Risk): On day 1 of week 4, participants will receive 0.1 mg of clonidine followed 20-30 min later by 6.25 mg of oral NTX. If tolerated, the person will return on day 2, receive 0.1 mg of clonidine followed 20-30 min later by 6.25 mg of oral NTX. On day 3, participants will receive 12.5 mg of NTX 20-30 min after clonidine. (For those who do not start induction until day 2 or 3: Starting on day 2, NTX will be given at the 6.25 mg dose 20-30 min after clonidine. On day 3, NTX will be given at the 12.5 mg dose 20-30 min after clonidine.) On day 4, 25 mg of NTX will be given 20-30 min after clonidine. If 25 mg is tolerated, then on the morning of day 5, participants will receive the depot NTX injection. (Participants have up to day 3 of week 4 to start the transition to NTX. For those who do not start induction until day 2 or 3: Starting on day 2, NTX will be given at the 6.25 mg dose 20-30 min after clonidine. Starting on day 3, NTX will be given at the 12.5 mg dose 20-30 min after clonidine. In such cases, dosing/administration on subsequent days will be as specified above.) Those

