At every visit, participants are asked whether they are experiencing any symptoms. The onset, duration, quality, and severity of any symptoms are recorded on the *Symptoms Form* and tracked to resolution. If symptoms are severe, then the medical staff is notified immediately. These symptoms are also discussed at weekly team meetings to ascertain whether the symptoms meet criteria for an adverse event. If so, attribution and severity are also determined.

The hypothesis posed under **Specific Aim 1** (regarding efficacy and tolerability of GBP during and immediately following BUP detox) will be tested by comparing drug-screen results, withdrawal measures, craving, sleep quality and adverse events between GBP and placebo groups during weeks 2-3 and day 1 of week 4. The hypothesis posed under **Specific Aim 2** (regarding acceptability/feasibility of transition to NTX therapy) will be tested by determining retention, reasons for dropout, drug-screen results and side effects during the oral NTX induction (week 4) and depot NTX therapy (weeks 4-8). Queries posed under **Specific Aim 3** (regarding prognosticators) will determine whether salient factors such as sex, other drug use, dependence diagnoses, distress tolerance measures, caffeine use, etc.: **a)** differentially impact response to GBP vs. placebo on outcomes during detox, **b)** are associated with differential outcomes during transition to NTX and **c)** are associated with differential longer-term outcomes at week 16.

- J. Timeline. We estimate that we will develop standard operating procedures during months 1–3 and enroll 2-4 participants/month during months 4–53, allowing for major holidays and staff vacations. All study procedures will be completed by month 55 and follow-up interviews by Month 58. We will complete data analyses and manuscript preparation by Month 60. These data, if positive, will be used to support further research on adjunct GBP during BUP detox as well as provide preliminary feasibility data for outpatient transition to NTX therapy.

8. Data Analysis Methods:

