occurred during gabapentin induction that were at least possibly study-related and showed a greater incidence in the gabapentin than placebo group: nausea/vomiting (gabapentin: N=2/16; placebo: N=1/14), somnolence (gabapentin: N=2/16; placebo: N=0/14), sleep disturbances (gabapentin: N=2/16; placebo: N=0/14), loss of motor skills (gabapentin: N=1/16; placebo: N=0/14), and lightheadedness (gabapentin: N=1/16; placebo: N=0/14). All events were mild and did not require an intervention, except for the lightheadedness, which occurred on day 4 during induction onto gabapentin. Even though vital signs were within the normal range, because this was a pilot study, a conservative approach was used and the gabapentin induction discontinued for this participant. Thus, we anticipate no pharmacokinetic interactions between these agents. There has also been one case study looking at gabapentin and buprenorphine and there was no adverse reaction. This case study was based on a previous 2006 review that showed that gabapentin produced a decrease in opioids consumed postoperatively [166, 167]. Nevertheless, based on the 12/19/19 safety report by the FDA, serious breathing difficulties may occur as a result of combined use of gabapentin and opioid pain medicines.

5. Clonidine. The use of clonidine to alleviate symptoms of opioid withdrawal is a standard clinical practice. Clonidine produces side effects such as dry mouth, drowsiness, sedation, dizziness, headache, fatigue, and changes in heart rate and blood pressure. The dose employed is within the recommended daily dose range [168].

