For data during the BUP taper (weeks 2-3), dependent variables obtained at several time points (e.g., urine sample results for opioids, opioid withdrawal symptoms scores) will be entered into random regression models, also known as hierarchical linear models (HLMs), to determine whether scores change differentially across treatment groups [154, 155]. Continuous data will be analyzed longitudinally with MIXREG, an HLM modeling program for continuous measures [156]. Dichotomous urine results (i.e., negative or positive) will be analyzed longitudinally using the SAS procedure GLIMMIX, which allows an HLM modeling program for ordinal outcome measures [157]. We will use all available data in our analyses and will make no attempt to interpolate missing data. HLM methodologies fit a regression line for each participant, effectively interpolating missing data, before deriving final estimates. This approach of modeling repeated measures is specifically designed for use in repeated measures designs with missing data, allowing for intra-participant serial correlation and unequal variance and covariance structures over time. These problems, common to clinical trial data, are solved by incorporating available trend data for each individual with information on the behavior of the group from which the participant is drawn. If there are any significant baseline differences, the variable will be added as a cofactor in the HLM analyses. We will examine differences in retention using Kaplan-Meier Survival Analysis. Analyses will be done on those who participated long enough to start the BUP taper, as well as during GBP induction to detect possible differential dropout before the taper. To determine whether treatment group differences occurred in 1) success of retention from the BUP detox to the NTX transition and 2) eligibility to undergo oral NTX induction, we will build 2 X 2 contingency tables using percentages of participants in the GBP vs. placebo groups who 1) return on day 1 of week 4 versus drop out after completing the taper, and 2) test negative versus positive for opioids. The type, severity, and frequency of adverse events will be compared across groups. All analyses will employ a significance level of $\alpha = 0.05$, and all tests are two-tailed.

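### The Aim 1 adverse-event comparison is windowed in Protocol 7.I to weeks 2-3 and day 1 of week 4, so as stated there it omits all five gabapentin escalation days; Protocol Section 8 and the SAP give no window and should be aligned

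*Protocol*

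**What the plan says.** - Protocol Section 3 makes good tolerability of GBP part of the Aim 1 hypothesis.
- Protocol 7.I, in the paragraph that links each aim to its test, says the Aim 1 hypothesis (efficacy and tolerability) will be tested by comparing several measures, among them "craving, sleep quality and adverse events between GBP and placebo groups during weeks 2-3 and day 1 of week 4". This is the only place in either document that sets a period for the Aim 1 adverse-event comparison.
- Protocol 7.C gives the start of study capsules: "The initial dose of GBP at 100 mg will be given on day 3 of week 1". Escalation ends with "600 mg BID on day 6, and 800 mg BID (1,600 mg/day) on day 7 of week 1".
- Protocol 13.4 describes the pilot. It lists events that "occurred during gabapentin induction that were at least possibly study-related and showed a greater incidence in the gabapentin than placebo group". One of them, lightheadedness on day 4 of induction, led to GBP induction being discontinued for that participant.
- Protocol Section 8 and the SAP (Specific Aim 1) say that adverse events will be compared between the arms, with no period attached. Both name the induction period once, in the sentence on retention: "as well as during GBP induction to detect possible differential dropout before the taper".
- Under Aim 2, Protocol Section 8 and the SAP compare adverse events between arms for the week-4 oral naltrexone (NTX) induction. For the later NTX phase, adverse events are only to be recorded and summarised.

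**The concern.** A tolerability comparison should cover the period in which people are first exposed to the drug and the dose is being raised. The window in 7.I opens the day after escalation ends. Events that begin and resolve during escalation would not be counted, and anyone who leaves during escalation contributes nothing to the comparison. If such events or departures are more common on GBP, leaving them out favours GBP. What is at stake is the tolerability half of the Aim 1 conclusion. The primary outcome, opioid-positive urines, is not affected.

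**Working it through.** The documents give no sample size, power or threshold specific to the adverse-event comparison, so there is no plan figure to reproduce. The check has three parts.

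**1. Window against dosing schedule.** Count week 1 day 1 as study day 1.

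- Escalation (Protocol 7.C), total daily dose: day 3, 100 + 100 = 200 mg; day 4, 2 × 200 = 400 mg; day 5, 2 × 400 = 800 mg; day 6, 2 × 600 = 1200 mg; day 7, 2 × 800 = 1600 mg.
- Window (Protocol 7.I): weeks 2-3 are days 8-21, and week 4 day 1 is day 22. That is 22 − 8 + 1 = 15 days.
- Escalation days inside the window: 0 of 5.
- GBP/placebo days from first dose to week 4 day 1: 22 − 3 + 1 = 20. Days omitted: 20 − 15 = 5, and 5/20 = 25%. All five are escalation days.

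**2. What the pilot reports for that period (Protocol 13.4).**

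| Event during induction | GBP | Placebo | Fisher two-sided p |
|---|---|---|---|
| Nausea/vomiting | 2/16 (12.5%) | 1/14 (7.1%) | 1.0 |
| Somnolence | 2/16 (12.5%) | 0/14 | 0.49 |
| Sleep disturbances | 2/16 (12.5%) | 0/14 | 0.49 |
| Loss of motor skills | 1/16 (6.3%) | 0/14 | 1.0 |
| Lightheadedness (dosing ended) | 1/16 (6.3%) | 0/14 | 1.0 |

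The totals are 2 + 2 + 2 + 1 + 1 = 8 reports among 16 GBP participants and 1 among 14 placebo participants. One person may account for several reports. As an example of the test, for 2/16 against 0/14 the two-sided p is (C(16,2) + C(14,2))/C(30,2) = (120 + 91)/435 = 0.49. The list is restricted to events that were more frequent on GBP, so the total of 8 against 1 does not estimate the overall difference between arms.

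**3. The passages side by side.** Protocol 7.I gives a window that excludes week 1. In Section 8 and the SAP the adverse-event sentence has none. The Aim 1 paragraph there opens with data from the taper in weeks 2-3, but that phrase introduces the repeated-measures models. The paragraph names GBP induction only for dropout. Protocol 7.B defines the detox phase as weeks 1-3, so week 1 falls within the phase that Aim 1 is about. An analyst could follow 7.I and exclude week 1, or follow the SAP sentence and include it. Nothing in the text settles which.

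**The case against.** The best case for the plan has four parts.

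- **The analysis sections do not restrict the comparison.** This stands in part. The adverse-event sentence in Section 8 and the SAP is open, and symptoms are asked about at every visit, so week-1 events are recorded and could be included. But no text extends the Aim 1 comparison to week 1, and the one text that sets a period leaves it out.
- **Loss during escalation is already examined.** This stands. Retention is compared between arms during GBP induction, and the Endpoint Rating Form records the reason for termination. That picks up people who leave. It does not pick up events in people who stay.
- **Much intolerance would still show inside the window.** This stands in part. Full dose is first taken on day 7 of week 1. The dose-reduction and discharge rules in 7.C refer to side effects at that dose or at 1200 mg/day, so many of those decisions would fall in week 2 or later. Symptoms are followed to resolution, so persistent ones may carry into week 2.
- **Later periods are not ignored.** This stands. Week-4 events are compared between arms under Aim 2, and side-effect scores in weeks 4-12 enter longitudinal models.

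A reader might infer more than this: that week-1 events are certain to be excluded, that everyone intolerant of escalation has left before counting starts, or that the pilot counts can be scaled up to predict how many events and stops would be missed. The documents do not support these readings. The SAP sentence is open. The stopping rules are mostly tied to doses reached at the end of week 1. The pilot list is short and selected for being higher on GBP. The pilot stop is described as a conservative choice made because it was a pilot, whereas this trial has a dose-reduction step.

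**Conclusion.** The point holds as a conflict, or at best an ambiguity, between Protocol 7.I and the analysis sections. If 7.I is followed, the Aim 1 adverse-event comparison omits all five escalation days, which are 25% of the GBP/placebo days up to week 4 day 1, and leans toward concluding that GBP is well tolerated. The day counts rest on the standard schedule in 7.C. The direction of the lean rests on the pilot pattern, which is weak evidence: small counts, no event type significant alone, and events listed only because they were higher on GBP. Because 13.4 lists only induction events, it cannot show that induction is the worst period, only that the reported excess lies there. The size of the effect on the trial's tolerability result cannot be derived from the documents. The separate dropout comparison and the Aim 2 comparison for week 4 limit the damage but do not replace a week-1 adverse-event comparison. It should be corrected before the arms are compared.

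**What to change.** In Protocol 7.I, and in the Aim 1 adverse-event sentence of Protocol Section 8 and the SAP, use the same three statements:

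1. The between-arm adverse-event comparison starts at the first GBP/placebo dose (week 1 day 3).
2. It includes everyone who took at least one dose, by randomised arm. This needs saying because Section 8 and the SAP also refer to an analysis group of those who reached the start of the taper, and it is unclear whether that group applies to adverse events.
3. Escalation is reported separately from the taper period.

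Preferably, also give a between-arm adverse-event summary through the last GBP/placebo dose (week 6 day 2), because adverse events in the NTX phase, which includes the week-5 GBP step-down, are otherwise only recorded and summarised.

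The cost is a few lines of text and one more table. Symptoms are already asked about at every visit, so no new data are needed. The tolerability result may look less favourable.

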Participants who successfully transition to NTX injection in week 4 will be offered the opportunity to receive one additional NTX injection in week 8. In order to be eligible for the second NTX injection, participants submit a urine sample that may need to be opioid-negative to receive NTX injection during week 8. If the urine sample is positive for opioids then the decision to give the second NTX injection will be made by a study physician. If the study physician determines that the participant will not receive the second NTX injection, they will be referred to appropriate alternative treatment, if desired. Otherwise, participants continue in the study as before, attending weekly clinic visits for individual psychotherapy and completion of assessments. All participants will attend their last clinic visit during week 12 to complete final assessments, terminate therapy, and receive aftercare referrals as determined during the course of treatment. A follow-up interview will be conducted during week 16 (+/- 1 week). Participants will receive an appointment reminder at least one day prior to each appointment during the NTX phase to increase attendance. Participants will be asked to supply names and phone numbers of at least two stable contact people whom staff can call if the participant can't be reached post-participation. Staff will maintain at least monthly contact with participants who have been discharged from the trial to enhance follow-up rates. In advance of the scheduled follow-up appointment, a reminder letter will be sent to each participant's most recently recorded address.

Assessments will typically be obtained once or thrice weekly (more often during week 4). A supervised urine sample will be obtained and self- and observer-ratings completed. Blood samples will also be drawn during week 4 to determine buprenorphine and gabapentin levels.

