- F. Maintenance of the Double Blind - A code will be kept in a locked cabinet, in a special file in the data manager’s or PI’s office, and pharmacy matching participants with the active/placebo study medications. This code will be available 24 hours a day and will be broken at the request of outside health professionals in the event of a medical emergency. To prevent any of the investigators from inadvertently discovering the medication assignments of other participants in the special file needs to be opened, a psychiatrist not directly involved with the study participants will open the special file. Once the code is broken, that participant will be dropped from the study. Although we do not anticipate difficulties maintaining the double blind, we will evaluate the adequacy of the double blind by having each participant and a research staff member report the medication (placebo or gabapentin) they believe is being administered.
- G. Counseling Guidelines - Several components of Behavioral NTX therapy [135] will be employed in the present study. During the BUP/GBP induction and detox phase, all participants will be scheduled to meet weekly, either in person, via telephone or video conference, with a research therapist typically for 60 minutes. Content of these sessions will include education and support, medication management, techniques to enhance motivation for abstinence or NTX therapy, and review of contingency management procedures. The session also provides an opportunity to review critical issues and problem areas. During NTX treatment, weekly sessions with the research therapist will include Cognitive Behavioral Treatment, manual-driven [136, 137] as a controlled element of the study. Modules will focus on relapse prevention and engagement in community support groups (e.g., Narcotics Anonymous). Although the involvement of a significant other in the treatment process will be encouraged, it will not be required for participation. The research therapist will monitor number and duration of scheduled treatment sessions, including frequency and reason for extra-session telephone calls, subjects’ involvement in any ancillary treatments, and other clinically significant events and formal treatment concurrent with their study treatment (including self-help meetings). At the end of the study, participants will be given treatment referrals.

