Specific Aim 3: Identify prognosticators of treatment outcomes. Predictors of treatment efficacy during each phase will be examined using baseline assessments (e.g., sex, level of opioid use, distress tolerance scores, etc.). We will evaluate general predictors of successful outcomes (with success as defined above) regardless of treatment type and predictors of differential response to treatments. Depending on the distribution of participants with moderate versus severe opioid dependence, severity of opioid dependence will also be examined as a prognosticator. Our basic analytic strategy will be to dichotomize groups into the presence and absence of a dichotomous predictor variable (e.g., female or alcohol dependence diagnosis) and then to examine the relative predictive values on treatment outcomes by adding each factor to the log linear analyses for single time point outcomes and HLM for longitudinal measures such as frequency of self-reported drug use, opioid-negative urines and craving measures. Each continuous measure (e.g., HAM-A, distress tolerance scores) will be entered as a covariate in the above analyses.

Longer-Term Outcomes. Continuous data from the 16-week follow-up interview will be initially entered into repeated measures ANOVA's with group (GBP vs. placebo), successful completion of detox (yes vs. no), successful induction onto oral NTX therapy (yes vs. no), and successful transition to depot NTX therapy (yes vs. no) as factors. Dichotomous follow-up data will be entered into Chi² tables for each phase. Longitudinal data captured during each phase of the study and at follow-up will be entered into random regression models as above, and piece-wise comparisons will be made between each phase. For all analyses, a p value <0.05 will be used to infer statistical significance.

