7. Research staff members monitor participant's status on at least a thrice-weekly basis during weeks 1-4 and weekly during weeks 5-12. The research counselor will monitor psychiatric symptoms such as depression and anxiety on a weekly basis. Should symptoms worsen, the study physician will evaluate the participant to determine whether he/she could safely continue in the study. We will evaluate suicidality using the Columbia Suicide Severity Rating Scale during either screening or intake and as clinically indicated thereafter. Those who answer yes to the second question regarding current (meaning last 30 days) suicidal thoughts AND to at least one of questions 3, 4, and 5 about plans or intention to attempt suicide in the past month or answers Yes to question 6 in the past 12 months will be excluded during screening. If current suicidal ideation or a suicide attempt occurs during the study, the physician will be notified, campus police and/or MEMS called (if this occurs on campus) or 911 called (if this occurs off campus) and the participant removed from the study. Participants will be given telephone numbers to call 24 hours a day in case of emergency. An on-call study physician will be available at the after-hours number.
8. Confidentiality will be protected by having all records identified by code number only, with the master file that matches subjects' names with their study doses kept under lock by the data manager and pharmacy. To prevent any of the investigators from inadvertently discovering the medication dose assignments of participants, drug records will be maintained by ID code only in the pharmacy and will be made accessible to research staff only after a participant has completed the study. A Certificate of Confidentiality will be obtained from the Department of Health and Human Services when the protocol is approved by the IRB and will be submitted to the IRB prior to participant enrollment.

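### Protocol section 14.B.8 lets research staff see drug records as each participant completes, and nothing in the protocol or SAP defers this to the end of the trial

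*Protocol*

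**What the plan says.** Protocol section 14.B.8 keeps drug records in the pharmacy by ID code. The file linking names to study doses stays locked with the data manager and pharmacy. The stated purpose is "To prevent any of the investigators from inadvertently discovering the medication dose assignments of participants". The same sentence then sets the time of release: the records "will be made accessible to research staff only after a participant has completed the study".

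The group given access is the group that follows current participants. Section 14.B.7 states: "Research staff members monitor participant's status on at least a thrice-weekly basis during weeks 1-4". Table 1 lists research staff as raters of the COWS and of both Hamilton scales, including at week 16.

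Section 7.F covers locked storage of the code and emergency code breaks. It also plans a test of the blind: "we will evaluate the adequacy of the double blind by having each participant and a research staff member report the medication" they believe is being given.

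Section 7.B places two events at the end of participation. The first is week 12: "All participants will attend their last clinic visit during week 12 to complete final assessments". The second is a follow-up interview at week 16, give or take a week. No passage says which of these makes a participant *completed*, or how a dropout is classed.

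**The concern.** A blind in a trial with staggered entry has to hold until the last assessment of the last participant. Release participant by participant lets staff build up a set of known arms, each paired with side effects and withdrawal they saw themselves, while they go on rating others. Two things could follow. Staff could guess the arms of current participants better. And because the urn scheme in section 7.E adjusts allocation probabilities to the earlier composition of the groups, knowledge of past assignments carries some information about the next one.

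The measures open to this are those resting on staff judgement: the COWS and Hamilton ratings, the attribution of adverse events after the weekly team review (section 7.I), and the staff-guess check of the blind, which would partly record what staff had learned from finished cases.

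**Working it through.** **1. Does any text defer access?** The relevant places, taken in turn:

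- Section 7.F: locked code and emergency code break; no end-of-trial release time.
- Section 14.B.11: an individual code break on incarceration of at least 3 days; nothing on general release.
- Section 15.A: before analysis the data are checked and corrected, and the data manager attaches study condition to the IDs. No database lock is named, and earlier access to pharmacy records is not barred.
- Section 15.D: DSMB reviews and interim analyses; nothing on when the blind is lifted for staff.
- SAP: silent on lifting the blind.

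So 14.B.8 is the only rule on general release to research staff, and it works per participant.

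**2. How much of the trial lies after the first possible release?** The plan gives no figure to reproduce, so this is derived from its timeline.

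Inputs: 150 participants (section 6); enrolment in months 4 to 53, that is 50 months, at 2 to 4 per month (section 7.J); completion at week 12 or week 16 (section 7.B); 4.345 weeks per month.

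- Average rate: 150 / 50 = 3 per month.
- Entered before the first entrant completes = rate × weeks / 4.345.
  - Week 12: 3 × 12 / 4.345 = 8.3.
  - Week 16: 3 × 16 / 4.345 = 11.0.
- Entering afterwards: 150 − 11.0 = 139.0 to 150 − 8.3 = 141.7, or about 93% to 94% of 150.
- At 2 to 4 per month, the number entered before the first release runs from 2 × 12 / 4.345 = 5.5 to 4 × 16 / 4.345 = 14.7.

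These figures assume that the first entrant stays to week 12 or 16 and that the record is opened as soon as it may be. If dropouts count as *completed* and their records open when they leave, the first release could come sooner.

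**3. The participant's own week-16 data.** If *completed* means the week-12 visit, records may be opened about 4 weeks before that person's follow-up. Table 1 schedules staff-rated COWS and Hamilton scales at week 16, and section 8 (Longer-Term Outcomes) and the SAP analyse continuous week-16 data with treatment group as a factor. If *completed* includes week 16, this participant's own ratings are safe. Neither reading protects later participants.

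**4. How delayed would disclosure be under an end-of-trial rule?** Follow-up interviews finish by month 58 (section 7.J).

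- First entrant, completing at week 16: 58 − (4 + 16 / 4.345) = 50.3 months.
- First entrant, completing at week 12: 58 − (4 + 12 / 4.345) = 51.2 months.
- Someone who leaves at the start of month 4: 58 − 4 = 54 months.

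**The case against.** The best defence is that the harm is indirect. The rule allows access and does not order it. It opens only finished participants' records. The primary outcome is illicit opioid use verified by urine assay, on which a rater's belief has little influence. Any effect needs a chain: staff open records, learn patterns, guess better, then rate differently. The documents show only the first permission. There are also partial safeguards: records held in the pharmacy by ID code, study condition attached to the data only before analysis, and a check of the blind that could detect staff guessing above chance. Gabapentin is tapered in week 5 and all participants receive placebo on the first two days of week 6 (section 7.C), so arm-related side effects are visible only early, and week-16 ratings bear only on longer-term outcomes. All of this stands and limits the point. None of it closes the gap in 14.B.8.

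Three stronger readings are tempting and not supported:

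- *That 14.B.8 contradicts section 7.F.* Section 7.F guards against "inadvertently discovering the medication assignments of other participants" when the file is opened for an emergency. Section 14.B.8 governs records of finished participants. The events differ; at most the two share a purpose.
- *That assay results already unblind staff.* Only urine from the gabapentin group goes for riboflavin assay (section 7.I), and research staff enter riboflavin and gabapentin results (section 15.A). But the documents do not say when results return or whether those who enter them also rate. Samples are frozen, and riboflavin is a back-up measure (section 7.D).
- *That 139 to 142 participants would be rated with bias.* The count says when people enter, not whose ratings change.

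**Conclusion.** The gap is real and worth closing. As written, 14.B.8 permits research staff to learn arms one participant at a time during a planned 50 months of enrolment, and no other text prevents it. About 139 to 142 of 150 participants would enter after the first possible release, assuming 3 entries per month and completion at week 12 to 16. The documents allow no estimate of any resulting bias.

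The consequence is confined to staff-rated secondary outcomes, adverse-event attribution, the staff-guess check and some predictability of urn allocation. The last of these depends on how much staff know of the strata and balancing variables as well as of past arms. The week-16 problem depends on one reading of an undefined word. A reader might infer that the primary result is compromised or that the trial plans routine unblinding; the text supports neither.

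**What to change.** Reword section 14.B.8 so that drug records become accessible to research staff only after the last participant's week-16 follow-up is finished and the data are final for analysis. Since no database lock is described, section 15.A should state what *final* means. With that trigger, the meaning of *completed* for one participant no longer affects release. Leave the emergency and incarceration code breaks, and any DSMB access, as they are.

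As a minor corollary, assay the stored gabapentin and riboflavin samples, or enter their results, after the last follow-up, or have non-rating staff handle them. Freezing already makes late assay possible.

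The cost is a few sentences of protocol text and later disclosure of assignments: about 50 to 54 months later for the earliest leavers, counted to month 58, plus whatever time is needed to finalise the data.
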